## 1. Visit schedule

Table 1: Visit schedule

Visit schedule	V1 M1-M3 (Baseline)	V2 M4-M8* (Follow-Up)	V3 M9-M14 (Closure)
Demographic data			
Age	x		
Gender	x		
Place of residence	x		
Social characteristics			
Employment status	x		
Marital status	x		
Education level	x		
Living arrangement	x		
Disease history			
Date of disease onset	x		
Date of initial diagnosis	x		
Age at disease onset	x		
Duration of disease	x		
Date of death (if applicable)			
Family history			
Family members who are living with ALS	x		
Family members who died of ALS	x		
Family members who are living with FTD	x		
Family members who died of FTD	x		
Family members who are suffering from neurological/psychiatric disorder	x		
Family members who died of any neurological/psychiatric disorder	x		
Clinical classification			
ALS subtypes	x		
Region of onset	x		
Functional deficits and progression			
ALS Functional Rating Scale (ALS-FRS)	x	x(2)	x
ALS progression rate (loss of ALS-FRS per month)	x	x(2)	x
King's classification of clinical stages of ALS	x		x
Serum neurofilament light chain (sNFL)	x	x(2)	X(2)
Interventions and health care measures			
Use of PEG	x		x
Use of non-invasive ventilation	x		x

Use of tracheotomy	x		x
Provision of a manual wheelchair (1)	x		
Provision of complex power wheelchair (1)	x		
Provision of a communication device (1)	x		
Provision of assistive technology (1)	x		
Physical, occupational and speech therapy (1)	x		
Riluzol and symptomatic pharmacotherapy (1)	x		
Treatment expectation			
MYMOP2, measure yourself outcome profile	x	x(2)	x(2)
Molecular genetic analysis			
C9orf72	x		
FUS	x		
SOD1	x		
TARDP	x		

M: month, V: visit; 1 = subgroup of users of APST management platform, 2 = in subgroup of patients with SOD1 mutation data will be collected more frequently (up to monthly collection of existing data of sNfL; up to weekly self-assessment of ALS-FRS using the ALS-App in addition to on-site assessment of ALSFRS-R during site visits). In the main cohort of non-SOD1 patients the collection of sNfL data is limited to the visits V1 (baseline) and V2 (follow-up).

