### **4.3. Overall study duration and assessments**

The study will include ALS patients at specialized outpatient clinics (study sites). All subjects will undergo 3 assessments over a period of approximately 12 months. The assessment schedule will be as follows:

- Assessment at baseline: initial assessment of subjects including blood sampling and molecular genetic analysis
- Assessment at follow-up: follow-up assessment that is realized in a 6-month interval
- Assessment at the end of the study: final assessment after 10 to 14 months interval and optional

  

- Assessment for interim analysis: interim analyses performed for this study at variable time points, at least after all subjects complete the 6-month assessments.

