### **7. Withdrawal of subjects**

Subjects must be withdrawn from the study for any one of the following reasons:

- The subject withdraws informed consent
- The subject is unwilling or unable to comply with the protocol
- At the discretion of the investigator

The reason for the subject's withdrawal from the study must be recorded. In case of withdrawal before the end of the genetic investigation, another patient can be enrolled to surrogate the other.

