### 9.3. Disease history

Data on disease history will be collected as follows. Onset of ALS will be defined at time of paresis in extremities, dysarthria or dysphagia.

Table 4: Items used to describe the disease history

Item	Description
Date of onset	MM-YYYY
Date of diagnosis	MM-YYYY
Age of onset	YY
Duration of disease	MM
Data of death (if applicable)	MM-YYYY

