## **11. Statistical methods and analysis plan**

Descriptive statistics will be presented for each assessment of all subjects at study visit. Subgroup analyses by genetic or clinical criteria or other baseline characteristics will be performed. Secondary endpoints in the genetically defined subsets of ALS with confirmed SOD1 or C9orf72 mutations will be compared to genetically tested patients with ALS not revealing any ALS-associated mutation in any of the tested genes. Descriptive statistics will be used for the statistical analysis (frequency in percentage, mean, median, standard deviation in  $\pm$ , interquartile ranges (Q1, Q3), and ranges (min, max). The standardized mean difference (SMD) will be applied in this study. The SMD of each measure over up to 12 months will be estimated using the change in measure between each subject's assessments and within each individual. The standardized mean difference expresses the size of intervention effect. Difference of frequencies between two groups will be assessed by Fisher's exact test or Chi-square test, or within metric data by using the Shapiro-Wilk test, Kruskal-Wallis test and Mann-Whitney U-test. The Wilcoxon test will be employed for the analysis of statistical power of ordinal-scaled data, while metric data were subjected to the t-test (ALS-FRS, MYMOP). This analysis applies to the comparison of genetically defined subsets of ALS (baseline characteristics and changes over time). The analysis of follow-up data is limited to complete

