cases, since not all patients are expected to complete end-of-study assessments due to disease progression, e.g., death. It is aimed to compare the baseline characteristics and the proportion of death between those who completed and not those not completed 6 months and 12-month assessment. Statistical significance will be ascertained by according to an error risk of up to 5% (p-value < 0.05). Associations for the clinical outcomes will be assessed by linear regression models adjusted for potential confounding factors. Results of the longitudinal observations will be also controlled for the influence of any covariate (sex, age, intervention history). Longitudinal analysis by means of group comparisons will be applied by using a multivariate analysis. 95% confidence intervals with p-values will be reported. In order to draw conclusions from the samples with censored data, missing data records will be omitted and treated as missing values. Data analysis will be performed using SPSS (Version 25.0).

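### The 12-month comparison of death between completers and non-completers is fixed at zero in completers, and no time point is set for establishing vital status in the rest

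*Combined protocol and SAP*

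**What the plan says.** Section 11 confines the longitudinal analysis to subjects with complete data and gives this reason: "since not all patients are expected to complete end-of-study assessments due to disease progression, e.g., death". It then aims to "compare the baseline characteristics and the proportion of death between those who completed and not those not completed 6 months and 12-month assessment". Differences in frequency between groups are to be tested by Fisher's exact or chi-square test, with significance at p < 0.05.

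Table 1 labels the last visit "V3 M9-M14 (Closure"), and section 4.3 describes it as a "final assessment after 10 to 14 months interval". Section 4.1 gives participation of up to about 12 months, and nothing after V3 is described. Section 5.1 plans 2,000 subjects and expects more than 1,000 to complete the end-of-study assessment.

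Death appears as a data item in two places. In Table 1 the row "Date of death (if applicable") is the only item with no visit marked. In Table 4 (section 9.3) the item "Data of death (if applicable") has a month-and-year format and nothing more. Section 7 lists three grounds for withdrawal, among them "The subject is unwilling or unable to comply with the protocol", and requires the reason to be recorded. Death is not one of the three, and no status check after withdrawal is described.

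**The concern.** Comparing completers with non-completers is meant to show whether restricting the analysis to complete cases is likely to bias it. A comparison of deaths can do that only if either group could have produced deaths. At the 12-month assessment this is not so: attending V3 requires being alive, and section 11 itself names death as a cause of not attending. The outcome therefore partly defines the grouping.

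The informative quantity is how many enrolled subjects died, in which genotype group, and how many have unknown status. The plan does not specify that output, nor a procedure that would supply it for subjects who miss V2 or V3.

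The comparison of SOD1 and C9orf72 carriers with mutation-negative patients on progression and health care (sections 3.3 and 11) depends on this. If death or loss differs by genotype, the complete cases are selected differently in each group, and the 12-month death comparison would not reveal it.

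**Working it through.** The documents contain no power, event or mortality calculation, so there is no figure to reproduce.

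**1. Deaths among 12-month completers.** A V3 completer is alive at V3, and no observation after V3 is described. Recorded deaths up to V3 are therefore 0, whatever the true mortality.

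**2. What the planned test would return.** Inputs: N = 2,000 and more than 1,000 completers (section 5.1); Fisher's exact test and p < 0.05 (section 11). The test is taken as two-sided, since the plan does not state sidedness. With 0 deaths in completers and d in non-completers, the tail probability is close to (share of non-completers)^d, and it is doubled when the groups are equal.

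| Completers / non-completers | Approximation | Exact p | One death fewer |
|---|---|---|---|
| 1,000 / 1,000 | d = 6: 2 × 0.5^6 = 0.031 | 0.031 | 0.062 |
| 1,200 / 800 | d = 4: 0.4^4 = 0.026 | 0.025 | 0.064 |
| 1,400 / 600 | d = 3: 0.3^3 = 0.027 | 0.027 | 0.090 |

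Between three and six recorded deaths thus reach significance. At an assumed 12-month mortality of only 5% (no rate is given in the documents) there would be 2,000 × 0.05 = 100 deaths, all among non-completers.

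**3. The six-month comparison.** V2 completers can die before V3. Under a constant hazard and assumed 12-month mortality m, the proportion of those alive at month 6 who die by month 12 is 1 − (1 − m)^(6/12):

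- m = 5%: 2.5%
- m = 10%: 5.1%
- m = 20%: 10.6%
- m = 30%: 16.3%

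This group is not fixed at zero.

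**4. How firm the 12-month zero is.** It holds up to the date of V3. A subject seen at month 9 could die by month 12 with probability 1 − (1 − m)^(3/12), which is 1.3% at m = 5% and 8.5% at m = 30%. Such a death could be entered if it became known, but no procedure looks for it.

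**5. The non-completer side.** With 1,000 non-completers and a fraction a of deaths ascertained, the recorded proportion is 2,000 × m × a / 1,000. Neither m nor a is in the documents. Taking m from 5% to 30% and a from 0.25 to 1, the result runs from 2,000 × 0.05 × 0.25 / 1,000 = 2.5% to 2,000 × 0.30 × 1 / 1,000 = 60%. The range is too wide to support any statement on the size of an undercount.

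**The case against.** The strongest reply is that the analyses are exploratory, a zero in one column does no harm, and the share of non-completers known to have died is still useful description. A blank visit cell is also natural for an event-driven item, and known deaths can be entered from medical records. All of this stands. It does not make the 12-month comparison informative, and it does not supply a cut-off or a check for subjects whose status is unknown. The blank cell could be an extraction loss, but every other row keeps its marks and no text gives a time point.

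A reader might also infer more than the documents support:

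- **That the six-month comparison is equally empty.** It is not, as step 3 shows.
- **That this is the plan's only check on informative loss.** The same sentence compares baseline characteristics. Genotype, ALS-FRS, progression rate and King's stage are all collected at V1, so loss can be examined by genotype and severity.
- **That a patient too ill to attend is withdrawn, the death goes unrecorded, and the patient cannot be told apart from one who refused.** Section 7 requires the reason for withdrawal and lists withdrawn consent separately. It does not equate a missed visit with withdrawal, and it does not say that record capture stops. Remote self-assessment is also available (sections 8.1 and 8.2).
- **That recorded deaths would be about half the true number.** That follows only from assuming half are untraced.

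**Conclusion.** The point holds for the 12-month death comparison. Recorded deaths among V3 completers are zero up to V3 by construction, so the test result reflects the grouping and cannot inform on attrition bias. This rests on V3 being the end of observation, which is how sections 1 and 4.1 read; a 12-month horizon with active tracing would relax it slightly.

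The gap in ascertainment also holds, in a limited sense. Death is a listed item and known deaths can be captured, but without a time point, cut-off or systematic check an unknown status cannot be reliably separated from survival. The extent cannot be quantified from the documents.

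The consequence is confined to interpreting the complete-case longitudinal comparisons between genotype groups. Variant frequency at baseline, the primary endpoint, is untouched. The change should be made, but it does not threaten the study's main aim.

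**What to change.** In section 11, replace the 12-month death comparison with two outputs and keep the comparison of baseline characteristics:

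- the proportion dead by a fixed time from V1, for example 12 months, by genotype group and over all enrolled subjects, with unknown status as its own category;
- mutually exclusive reasons for non-completion (died, too ill to attend, withdrew consent, lost), by genotype group.

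In Table 1, assign vital status and date of death to one fixed time point for all enrolled subjects whose consent has not been revoked, taken from existing site records or the APST platform. The check should fall no earlier than the chosen cut-off, so that it also covers subjects whose V3 took place before it; the end of the V3 window at month 14 would serve for a 12-month cut-off.

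The cost is minor site work and a replaced sentence in section 11. The consent wording must cover the status check.

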## Study Synopsis

Tracking Number:

Protocol Title: Clinical characteristics, natural history, health care measures, and the frequency of genetic variants in the genes of SOD1, C9orf72, FUS and TARDBP in patients with sporadic and familial amyotrophic lateral sclerosis (ALS)

Version Number: 2.6

Study indication: Amyotrophic Lateral Sclerosis (ALS)

Study rationale: There is only limited data available on the frequency of genetic variants in patients with sporadic ALS (sALS) and familial ALS (fALS). In patients with sALS (patients without family history of ALS), genetic investigations do not belong to the standard of care. As a result, the patient's mutation status is commonly unknown. Even in patients with fALS (with known family history of ALS), screening for genetic mutations is not performed on a regular basis, due to lacking treatment options in the field of gene therapy. However, this paradigm is about to be changing as clinical trials on genetic medicines are ongoing and might result in the approval of new genetically investigated drugs in the future. This project is intended to investigate a large cohort of ALS patients on family history, clinical characteristics, health care measures and genetic variants in SOD1, C9orf72, FUS and TARDBP – the most commonly mutated genes in ALS. This cohort study will allow to determine the frequency of gene mutations in ALS patients in a real-world setting of ALS centers in Germany. Furthermore, the project shall enhance insights into potential differences between genetically defined cohorts by means of the course of disease and the provision of health care measures. The investigation of genetically distinct ALS cohorts is particularly relevant, as an improved understanding of the relationship between the genotype and the journey of disease is scientifically indispensable, in order to determine the therapeutic potential of future genetic therapies.

Objectives and Endpoints: Primary objective

- To identify the frequency of genetic variants in the genes of SOD1, C9orf72, FUS and TARDBP in patients with sALS and fALS

Secondary objectives

- To investigate the demographic and social characteristics
- To investigate the family history for ALS or FTD
- To investigate the clinical classification, functional deficits and progression

- To register interventions and health care measures including percutaneous endoscopic gastrostomy (PEG), ventilation therapy,

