#### **3.3. Additional objectives**

The additional objectives of this study are as follows:

- To investigate the demographic and social characteristics
- To investigate the family history for ALS or FTD
- To investigate the clinical classification, functional deficits, disease progression and health care measures in a subset of ALS patients with pathogenic variants in the genes of SOD1

or C9orf72 as compared to ALS patients with no ALS-associated mutations in the investigated genes

- To register available data on serum concentration of neurofilament light chain (sNfL)
- To register the history of interventions and health care measures including percutaneous endoscopic gastrostomy (PEG) and ventilation therapy
- To register the provision with assistive technology devices, symptomatic pharmacotherapy and physical, occupational and speech therapy
- To identify patient's treatment expectations towards ALS therapy using the Measure Your Medical Outcome Profile (MYMOP2)

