## 9.7. Interventions and health care measures

Data on clinical interventions and health care measures will be collected as follows:

*Table 8: Items used to describe clinical interventions and health care measures*

Item	Description
Percutaneous endoscopic gastrostomy (PEG)	Y/N Date of provision (MM/YYYY)
Non-invasive ventilation (NIV)	Y/N Date of provision (MM/YYYY) Usage up to 8 hours per day Usage 8 to 16 hours per day Usage more than 16 hours per day
Invasive ventilation (IV)	Y/N Date of provision (MM/YYYY)
Provision of manual wheelchair (1)	Y/N Date of provision (MM/YYYY)
Provision of complex power wheelchair (1)	Y/N Date of provision (MM/YYYY)
Provision of augmented communication device (1)	Y/N Date of provision (MM/YYYY)
Provision of assistive technology (e. g. robotic arms), (1)	Y/N Date of provision (MM/YYYY)
Physical therapy (2)	Y/N Treatment units per week
Occupational therapy (2)	Y/N Treatment units per week
Speech and swallowing therapy (2)	Y/N Treatment units per week
Pharmacological therapy (3)	Riluzol, Y/N Symptomatic drugs, number of medicines

(1) Data will be obtained in a multi-center subset of up to 300 participants

(2) Data will be obtained in a single-center subset of up to 100 participants

(3) Data will be obtained in a multi-center subset of up to 200 participants

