Patients who refuse to be notified about study results will not be informed about the outcome of genetic analysis. This patient's directive explicitly includes pathogenic mutations that might be of diagnostic or therapeutic relevance. The patient's directive of notification of all genetic study results will include normal findings (no or benign variants) genetic, genetic variants of unknown significance and pathogenetic mutations (likely pathogenic or pathogenic genetic variants in the investigated genes of SOD1, C9orf72, FUS and TARDBP. Results of diagnostic relevance are defined as genetic variants being known to cause ALS or can increase the risk of ALS or can modify the phenotype of the disease including the progression rate. The finding of pathogenic variants can lead to the diagnosis of fALS although the disorder – given the negative family history of ALS – has prior been classified as sALS. The diagnostic relevance can extend to other family members as likely pathogenic or pathogenic mutations in the study at ALS genes might substantiate a genetic risk for ALS to first- and second-degree relatives of study participants. Therapeutic relevance is defined by the planning or performance of a phase 3 clinical trial, a planned or ongoing early access program or an expected approval of genetic medicine targeting one of the studied genes within the next 12 months. Currently, therapeutic relevance can be stated for mutations found in the SOD1 gene. Therapeutic relevance of C9orf72 and FUS can be expected within the next few years post-approval of this study protocol. The definition of diagnostic and therapeutic relevance and the scheme of notification of individual study results is provided in table 11.

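### Section 11 controls longitudinal results for an undefined intervention history; if this means PEG and ventilation, the adjustment can absorb part of a genotype difference in disease course

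*Combined protocol and SAP*

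**What the plan says.** Section 11 makes four statements that bear on this point.

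- Patients with SOD1 or C9orf72 mutations are compared with tested patients who have none, using tests without covariates: "This analysis applies to the comparison of genetically defined subsets of ALS (baseline characteristics and changes over time").
- A regression sentence follows that names no factors: "Associations for the clinical outcomes will be assessed by linear regression models adjusted for potential confounding factors".
- The next sentence names three covariates: "Results of the longitudinal observations will be also controlled for the influence of any covariate (sex, age, intervention history").
- Confidence intervals and p-values are to be reported.

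The term intervention history appears only there. The nearest wording is in section 3.3: "To register the history of interventions and health care measures including percutaneous endoscopic gastrostomy (PEG) and ventilation therapy". In Table 1 (section 1), PEG, the row "Use of non-invasive ventilation" and tracheotomy are marked at V1 and V3 with no subgroup footnote. Devices, therapies and drugs carry subset limits in the footnotes to Table 8 (section 9.7), for example "Data will be obtained in a multi-center subset of up to 300 participants".

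The synopsis and section 2.2 give the aim as insight into "potential differences between genetically defined cohorts by means of the course of disease and the provision of health care measures". Section 12.3.1, in defining diagnostic relevance, says variants "can modify the phenotype of the disease including the progression rate".

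**The concern.** A confounder of a genotype contrast would have to be associated with genotype without being a consequence of it. Germline genotype precedes every PEG and every ventilator, so these cannot play that part. They sit downstream: patients who decline faster tend to need them sooner.

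They also overlap the outcomes. Section 9.6.1 says the ALS-FRS covers interventions for nutrition and ventilation. Section 9.6.3 defines King's stage 4 by failure of nutrition or respiration. Section 3.4.2 lists PEG, non-invasive ventilation and tracheostomy as endpoints.

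If carriers of a variant decline faster and so receive more interventions, a model holding intervention use constant compares them with non-carriers who also declined fast. Part of the difference then disappears. A reader who sees the gap shrink after adjustment may conclude that confounding explained it. This is the only longitudinal adjustment with named covariates, and no model with sex and age alone is written.

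The missing cut-off visit matters too, because use that begins between V1 and V3 could enter the covariate.

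**Working it through.** The plan gives no figure that depends on this point, so there is nothing to reproduce. The check has two parts: what the term most likely means, and how large the effect could be.

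**Meaning.** Section 3.3 ties the history of interventions to PEG and ventilation, though its wording allows other items. Tables 1 and 8 show that these are the only interventions collected without a subset limit. Any other reading would confine the adjusted analysis to at most 300, 200 or 100 participants. PEG and ventilation is therefore the most natural reading, but not a certain one.

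**Inputs from the documents.** 12-month observation; ALS-FRS from 0 to 48 (9.6.1); about 1,000 of 2,000 completing, that is 50% (5.1).

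**Assumed inputs.** Monthly loss is normal with mean 0.9 in non-carriers and 1.2 in carriers, SD 0.7. Carriers are 10%. Uptake is 20-40% by month 12, or 10-20% at V1. Uptake has odds ratio OR per 5 points lost. The intervention itself costs 0 or 4 scale points.

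**Formula.** Let D be the unadjusted carrier minus non-carrier difference in 12-month change, m1 and m0 the uptake proportions in carriers and non-carriers, and b the pooled within-group slope of change on uptake. Least squares gives

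D_adj = D - b × (m1 - m0), and share removed = 1 - D_adj / D.

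**Worked case** (OR 2, 40% uptake, no score cost, unbounded score, no dropout):

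- D = -12 × 0.3 = -3.60.
- Numerical integration gives m1 = 0.487, m0 = 0.390, b = -7.73.
- D_adj = -3.60 + 7.73 × 0.097 = -2.85.
- Share removed = 1 - 2.85/3.60 = 21%.

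**Share removed over the assumed range:**

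| OR per 5 points | History to month 12 | Baseline-only history |
|---|---|---|
| 1 | 0% | about 0% |
| 1.25 | 2-7% | 2-3% |
| 1.5 | 7-15% | 4-8% |
| 2 | 16-28% | 8-14% |
| 3 | 28-42% | 10-20% |
| 4.5 | 36-51% | 11-22% |

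The baseline-only column depends on how much loss is assumed to precede V1, which the documents do not give.

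**How extreme the last row is.** The SD of 12-month loss is 12 × 0.7 = 8.4 points. From -1 SD to +1 SD is 16.8 points, so OR 4.5 multiplies the odds of uptake by 4.5^(16.8/5) = 157. OR 2 already gives 2^(16.8/5) = 10. The 51% needs OR 4.5, 40% uptake and the 4-point cost together.

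**Other assumptions.**

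- A second simulation used 6.5% carriers, a genotype difference of 0.2 or 0.4 points per month and an SD of 0.5 or 0.8. It removed 0% with no association, and 1-5%, 5-14% and 16-34% at log-odds 0.5, 1 and 2 per point per month. Over 12 months those equal ORs per 5 points of exp(0.5 × 5/12) = 1.23, exp(5/12) = 1.52 and exp(2 × 5/12) = 2.30, in line with the table.
- With scores kept within 0-48 and 50% completers, one OR 2 example moved the change difference from -2.02 to -1.85 with V1 history (8%) and to -1.40 with month-12 history (31%). The section 9.6.2 progression rate moved from 0.265 to 0.237 (11%) and 0.178 (33%).
- For King's stage 4 at 40% versus 30%, a linear probability model loses 6-23% if the history covers 30% of stage 4 patients and 0-10% of the others. Much higher coverage gives larger shares, but the covariate then nearly restates the outcome.

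**Reversal.** Suppose carriers have less bulbar onset (10% versus 30%), bulbar onset raises uptake odds sevenfold, OR is 1, uptake is 40% and the cost is 4 points. The unadjusted -3.24 then becomes -3.60 after adjustment.

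**Null case.** With no genotype effect, the adjusted difference is zero within simulation error (at most 0.03 points).

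**The case against.** The plan never says that a total genotype effect is the target. Its aims speak only of differences and comparisons, and the section 12.3.1 remark is consent text. Because the ALS-FRS reflects nutrition and ventilation interventions, asking how course differs apart from their use is a legitimate secondary question. This stands: the documents leave the target unstated, so the adjustment cannot be called an error under every target.

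Section 11 already plans comparisons of change over time without covariates and describes the covariate control as additional. A reader might infer that the adjusted result will be the main one, or that no unadjusted contrast will be shown. The documents support neither inference, since no ranking is given.

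The sentence on potential confounding factors, read correctly, would leave PEG and ventilation out. It names no factors, however, while the following sentence names intervention history explicitly, so it does not settle the matter. Nor is it stated whether the three covariates enter together.

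Finally, all effect sizes are assumed and the evaluation is exploratory (3.4.2). Both points stand and limit the weight of the finding. They do not remove it, because the adjusted results will still be reported with intervals and p-values.

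**Conclusion.** The point holds conditionally. If intervention history means PEG and ventilation, and if uptake tracks progression, controlling for it can absorb part of any real genotype difference in ALS-FRS change, progression rate or King's stage. At an uptake odds ratio of 2 per 5 points lost, roughly 15-30% of the difference in 12-month change is removed with history up to month 12. With baseline-only history the figure is 8-14% in the setting calculated. Nothing is lost if uptake is unrelated to progression, and the direction can reverse if genotype affects uptake by another route.

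A reader might take from the table that the adjustment would halve genotype effects. That needs the most extreme combination of assumptions, and nothing in the documents points to it. The unadjusted comparisons and the primary objective (variant frequency) are not affected. The change should be made because a named covariate is unsuited to the comparison the protocol describes and the remedy is cheap.

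**What to change.** In section 11:

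1. State that the adjusted genotype contrast for ALS-FRS change, progression rate and King's stage uses sex and age. Both are already named, and neither follows from progression.
2. Show it beside the unadjusted comparison. This also covers the possibility that age partly reflects a genotype-related age at onset.
3. Define intervention history: which items, and up to which visit.
4. Report any model that includes it only as a labelled sensitivity analysis of direct-effect type. Note that even a direct-effect reading needs further assumptions about common causes of uptake and progression, such as region of onset.

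The cost is SAP wording and one extra model per outcome. No new data, visits or patients are needed.
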